Effect of preoperative single-dose tamsulosin on postoperative urinary retention after mid-urethral sling placement: a randomized, double-blinded, placebo-controlled trial

Principal Investigator
[name]

Clinical Research Supervisor
[name]

Sub-Investigator(s)
[name] MPH
[name]
[name]
[name]
[name] MHS
[name]

Sponsor
None

Site of Investigation
Northshore University Health System

Date of Protocol: 04/08/2023
NCT05753670

Protocol Version: 2

Purpose

The purpose of this study is to evaluate whether a single dose of preoperative tamsulosin may improve postoperative urinary retention rates determined by postoperative retro-fill voiding trial compared with placebo.

Background

Postoperative urinary retention has been defined as the inability to void despite having fluid in the bladder during the postoperative period (3). Urinary retention after pelvic reconstructive surgery requiring indwelling catheter or self-catheterization usage occurs in approximately 30-60% of patients postoperatively (1,2,3).

During a retro-fill voiding trial, the bladder is back-filled with a set amount of sterile water (often 300mL), the catheter is removed, the patient is permitted to void and the voided volume is compared with a bladder scan post void residual volume. “Passing” a voiding trial has previously been defined as voiding equal or greater than $\frac{1}{3}$ the residual volume, whereas others characterize “passing” as voiding at least 200mL and voiding a greater volume than the post-void residual volume (4). If the patient does not “pass” the voiding trial, the patient is characterized as having postoperative urinary retention and is discharged home with an indwelling catheter to prevent detrusor injury from bladder overdistention, pain and urinary tract infection (5).

Many women consider being discharged home with a Foley catheter to be a surgical complication and describe catheter use as the worst aspect of their surgery (1,6). Indwelling catheters are the leading cause of hospital-acquired urinary tract infections (UTIs), are often a source of embarrassment and inconvenience for patients, and often require additional office visits and healthcare utilization (8).

Tamsulosin is an alpha-adrenergic receptor blocker which is thought to increase smooth muscle relaxation and improve urinary flow (9). Current literature has been primarily focused on the effect of tamsulosin in men with benign prostatic hyperplasia, however may be beneficial in women as well with limited studies for postoperative urinary retention (9). Chapman, et al published a randomized control trial evaluating postoperative urinary retention after female pelvic reconstructive surgery (10). These patients underwent 10 days of tamsulosin (3 days preoperative and 7 days postoperative) and were found to have a 65% decrease in the urinary retention rate from 25.8% to 8.8% (10). Livne, et al published a study evaluating postoperative urinary retention decrease of 79.2% after postoperative administration of dibencyline (an alpha-adrenergic receptor blocker) in women undergoing hysterectomy (post-operative urinary retention rate of 18.75% in controls and 3.9% in the treatment group) (11). Additional studies have also been published evaluating postoperative urinary retention in men and women undergoing various surgeries and have demonstrated a decrease in postoperative urinary retention after tamsulosin administration from 72-88% compared with controls (12-14). These studies vary in tamsulosin administration from multiple days preoperative and postoperative to multiple doses preoperative and postoperative to a single postoperative dose, however no studies have been published in evaluating a single preoperative dose of tamsulosin and the effect on postoperative urinary retention (10-14). This has previously been studied as tamsulosin reaches a steady state in approximately 5 days, however when tamsulosin is given in a fasting patient, it can reach the maximum blood concentration in approximately 4-5 hours (10,15). As the majority of female pelvic reconstructive surgeries performed by our department are same-day surgeries, with patients being discharged the day

of surgery, we would like to investigate the effect of a single preoperative dose of tamsulosin on postoperative urinary retention and, by effect, home catheter usage after surgery. Tamsulosin is cost-effective at approximately \$2 per tablet (16). Despite primarily being prescribed for benign prostatic hyperplasia, tamsulosin has been found to be a safe and well-tolerated treatment for voiding dysfunction in women (9).

Postoperative urinary retention is common after pelvic reconstructive surgery with mid-urethral sling placement and is extremely bothersome to patients. Tamsulosin is a low-risk, well tolerated, cost-effective medication that studies have suggested may decrease the rate of postoperative urinary retention (9). No study to date has evaluated preoperative administration of single- dose tamsulosin for postoperative urinary retention in a randomized placebo-controlled trial.

Hypothesis

We hypothesize that providing preoperative tamsulosin will improve postoperative urinary retention rates determined by postoperative retro-fill voiding trial compared with placebo.

Objectives

The **primary objective** of this study is to evaluate whether preoperative administration of tamsulosin will decrease the rate of postoperative urinary retention after mid-urethral sling placement with or without concomitant prolapse surgery compared with placebo. The **secondary objective** of this study is to evaluate for any differences in hypotension, unplanned admission, postoperative UTI, or unplanned 30-day healthcare encounters after preoperative tamsulosin compared to placebo.

Specific Aims

1. Compare the postoperative urinary retention rates after preoperative administration of tamsulosin compared with placebo.
2. Compare differences in postoperative pain (postoperative nursing documentation performed in the recovery area based on a Likert scale of 0-10), hypotension (immediately postoperative) or postoperative UTI (UTI within 30 days of procedure) after preoperative administration of tamsulosin compared with placebo.
3. Compare time to Foley catheter removal and voiding trial in the recovery area between the two study groups.
4. Evaluate the difference in unplanned admission the day of surgery or unplanned admission within 30 days after surgery, unplanned office visits within 30 days after surgery or Northshore encounters within 30 days after surgery after preoperative administration tamsulosin compared with placebo. These medical encounters will include any need for additional medical treatment, phone calls, complications or patient concerns within 30 days postoperatively. This data will be collected via chart review.
5. Evaluate subjective measure of “feeling empty” after a void compared with PVR value.

Outcome measures

1. Primary outcome measure:
 - a. Determine the postoperative urinary retention rates after preoperative administration of tamsulosin compared with placebo. This will be determined immediately postoperative in the postoperative recovery room based on whether patients pass or fail their voiding trial described above. The result will be documented in electronic medical records and obtained from chart review.
2. Secondary outcome measures:

- a. Determine differences in postoperative pain, hypotension, postoperative UTI after preoperative administration of tamsulosin compared with placebo. This data will be obtained by electronic data pull and chart review.
- b. Determine time to Foley catheter removal and voiding trial in the recovery area between the two study groups which will be obtained by chart review of the documentation for Foley removal.
- c. Determine the difference in unplanned admissions, office visits or Northshore encounters within 30 days after surgery after preoperative administration of tamsulosin compared with placebo. This data will be collected via chart review.
- d. Determine correlation between subjective measure of “feeling empty” and PVR. This will be documented in the electronic medical record by the postoperative nursing staff along with the PVR result obtained from ultrasound in the postoperative recovery area.

Methods

This is a prospective randomized, double-blinded, placebo- controlled trial of patients who are undergoing elective mid-urethral sling placement with or without concomitant prolapse surgery with the Center for Pelvic Health at the Northshore University Health System.

Women presenting to our tertiary urogynecology clinic with stress urinary incontinence who decide to proceed with surgical treatment of stress urinary incontinence via a mid-urethral sling placement will be invited to participate in this study. This study will be discussed with the patient by their surgeon during their clinic initial screening visit or preoperative visit based on inclusion and exclusion criteria listed below. This study will involve no additional pre-operative tests or questionnaires, beyond our routine clinical pathway for women presenting with stress urinary incontinence. Written consent will be obtained.

During the initial clinic visit, patients will be provided information on the research study by their care provider and given the opportunity to ask any questions. Patients will then be given a consent form to take home and review, discuss with others and consider participation. At the second clinic preoperative visit, patients will have another opportunity to discuss the study and ask any questions to their care provider. At that point, patients will be given the opportunity to sign the consent form if they would like to participate in the study. Participation is voluntary. For patients who will not have a second preoperative clinic visit prior to surgery, during the initial clinic visit, the care provider will discuss the research study, provide a consent form to the patient to review and ask for permission from the patient to be contacted by a study team member. If permission is granted, a study team member will contact the patient via telephone to discuss the study further and allow for the patient to consider participation in the study and ask any questions. If at that time the patient decides to participate in the study, written consent will be obtained the morning of surgery. All consent documentation and research participation will be documented in the patient’s chart.

Patients who are undergoing a mid-urethral sling placement will be enrolled (after the previously described informed consent discussion) to receive either a single tablet of tamsulosin 0.4mg or a placebo in the preoperative holding area on the day of their scheduled surgery.

Randomization will occur by simple randomization (1:1 randomization) with a computer-generated random number list. The patient will be randomized to one of the two groups (preoperative tamsulosin 0.4mg tablet versus placebo). This random number list will be sent directly from the statistician to the pharmacy. The clinician will place an order for the preoperative trial medication and the pharmacy will

dispense either a single tablet of tamsulosin 0.4mg or placebo to the preoperative holding area according to the randomization list that the pharmacy has been provided by the statistician. The trial medication will be sent from the pharmacy to the preoperative area to be taken prior to surgery. The clinicians, preoperative and postoperative nursing staff, and the patients will be blinded to the trial group and medication.

After surgery, patients will then undergo a retro-fill voiding trial in the recovery area. The voiding trial will be performed as follows: using a Foley catheter placed in the OR, we will retro-fill the bladder with 300mL of sterile normal saline (using the catheter that is already in place, a trained nurse will fill the bladder with sterile normal saline), the catheter will be removed and the patient will be asked to void. The measured voided volume will be recorded and a bladder scan post-void residual (PVR) volume will be obtained. Patients will be asked if they "feel empty" as a subjective measure of voiding success. As described in prior studies, the patient will fail the voiding trial if voided volume is less than $\frac{1}{3}$ total bladder volume and PVR is greater than or equal to 200mL. Upon failing the voiding trial, the patient will be discharged home with a Foley catheter with plan for outpatient follow up for catheter removal in clinic, consistent with our current protocol. According to our current protocol, patients discharged with a Foley catheter can either remove the catheter at home in 48-72 hours after surgery or call our office to have it removed at the next available appointment within 2-5 days postoperatively.

We will then evaluate the rate of postoperative urinary retention after preoperative administration of tamsulosin compared with placebo. Any collected information will be de-identified.

The current rate of postoperative urinary retention at our institution based on chart review is 25%. Published data discussed above have described a postoperative urinary retention rate decrease of 65-88% (10-14). Based on a sample size calculation to achieve 80% power, to evaluate for a 65% decrease in our urinary retention rate (from 25% to approximately 8.8%) we will need to recruit 160 total subjects (80 per group).

Inclusion criteria

Mid-urethral sling placement (CPT 57228)

Exclusion criteria

Age <18

Planned combined cases with colorectal surgery, general surgery, or gynecology-oncology

Planned sling revision or history of prior sling placement

Known history of urinary retention

Concomitant intravesical botulinum injections

Known contraindication to tamsulosin

Variables

MRN

Age (at time of surgery)

Gravity and para

Race/ethnicity

Smoking status

Menopausal status

BMI

Comorbid conditions
 Diabetes
 Hypertension
 Other cardiovascular disease
 Respiratory disease
 Obstructive sleep apnea
 Chronic pain conditions

Prior hysterectomy
Prior abdominal surgery
History of prior prolapse surgery
Prolapse stage
Location of surgery (Highland Park Hospital, Evanston)
Type of anesthesia
ASA grade
Incontinence procedure
Mid-urethral sling placement: CPT 57228
Concomitant prolapse procedures
 Anterior colporrhaphy: CPT 57240
 Posterior colporrhaphy: CPT 57250
 Combined anterior and posterior colporrhaphy: CPT 57265
 Apical prolapse suspension
 Vaginal vault suspension
 Intraperitoneal: CPT 57283
 Extraperitoneal: CPT 57282
 Sacrocolpopexy: Minimally invasive (robotic-assisted and laparoscopic): CPT 57425

Concomitant procedures
 Hysterectomy
 Rectopexy

Intraoperative complications
Additional procedures (lysis of adhesions)

Intraoperative consultations

Length of procedure

Estimated blood loss

Surgeon
 Surgeon experience (< 5 years, > 5 years)

Total time in PACU

Time of day in ASU

Total time in ASU

Immediate postoperative complications
 Uncontrolled nausea
 Uncontrolled pain
 Hypotension
 Incisional bleeding

Postoperative pain scores upon admission to the ASU

Postoperative pain scores at discharge

Reason for postoperative admission (surgeon choice, comorbid conditions, nausea/vomiting, etc.)

Time from voiding trial to void

Subjective determination of “feeling empty”

Postoperative urinary retention

Postoperative urinary tract infection (UTI)

Unanticipated healthcare encounters

Urogynecology office visit (excluding voiding trial(s))

ED visit

Readmission within 30 days of discharge

Unplanned phone calls

Complications 30 days after discharge

Urinary tract infection

Reoperation

Venous thrombotic event

Statistical Methodology

A statistician from the NorthShore Research Institute will assist with statistical analysis. Data will be analyzed using SAS 9.4 (SAS Inc., Cary, NC). Demographic and clinical characteristics between groups will be compared using Student t-test (parametric) or Mann-Whitney U test (nonparametric) for continuous variables and Chi-squared test or Fisher exact test for categorical variables. Multivariable logistic regression models will be constructed to examine the relationship of an outcome with demographic and clinical covariates. Statistical significance will be defined at p-value < 0.05.

Literature review

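### Does the plan need a stated analysis population and a rule for randomised patients who have no recovery-room voiding-trial result?

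*Combined protocol and SAP*

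**What the plan says.** Under Outcome measures, item 1a, the protocol fixes when and where the primary outcome is read: "This will be determined immediately postoperative in the postoperative recovery room based on whether patients pass or fail their voiding trial described above". The Methods describe the test in one sequence: "After surgery, patients will then undergo a retro-fill voiding trial in the recovery area". Failure is then defined from a measured voided volume and a post-void residual, and a patient who fails goes home with a catheter.

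Other sections recognise that not every patient goes straight home. The Background says that "the majority of female pelvic reconstructive surgeries performed by our department are same-day surgeries", which is not all of them. The secondary objective is to "evaluate for any differences in hypotension, unplanned admission, postoperative UTI, or unplanned 30-day healthcare encounters after preoperative tamsulosin compared to placebo", and Specific Aim 4 begins "Evaluate the difference in unplanned admission the day of surgery". The Variables list records the reason for a postoperative admission.

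The Methods set the sample size at 160, 80 per group, for 80% power to detect a fall from 25% to about 8.8%, with no stated allowance for missing results. Statistical Methodology names the software, the tests (for categorical data, "Chi-squared test or Fisher exact test for categorical variables"), logistic regression and a 0.05 significance level. It does not name an analysis population, say that patients are analysed as assigned, or say what is done when the primary result is absent.

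**The concern.** The tablet is taken before surgery and the outcome is read after it, so surgery, complications and a decision to admit can all fall in between. An untested patient is neither a pass nor a fail under the definition. Hypotension and unplanned admission are also outcomes that the trial compares by arm. If either kept a patient from being tested, being untested could depend on treatment. Blinding does not prevent that, because the cause would be a drug effect rather than knowledge of the arm.

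Only about 27 retention events are expected, so a few patients handled one way or another could move the p-value. If the handling were chosen after the results were known, the choice could be challenged. Patients left out without a count by arm could also favour one arm unseen.

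**Working it through.** **Inputs.** From the Methods: 25% on placebo, about 8.8% on tamsulosin (a 65% reduction gives 0.25 × 0.35 = 8.75%), 80% power, 80 per arm. From Statistical Methodology: 0.05, taken as two-sided because the plan does not say. The documents give no number of untested patients, so all such counts below are assumptions.

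**1. The plan's own figure.** The unpooled formula is n = (1.960 + 0.842)² × [p1(1 − p1) + p2(1 − p2)] / (p1 − p2)².
- p2 = 0.0875: 7.849 × (0.1875 + 0.0798) / 0.1625² = 79.5 per arm.
- p2 = 0.088: 7.849 × (0.1875 + 0.0803) / 0.162² = 80.1 per arm, strictly 81 when rounded up.

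The arcsine formula at 8.8% gives 79.3, hence 80 per arm and 160 in total. The stated size is reproduced with every patient having a result.

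**2. Power if untested patients are left out, equally in both arms.** Exact power of the uncorrected chi-squared test, 25% versus 8.75%, by full enumeration:

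| Untested | Per arm | Power |
|---|---|---|
| 0% | 80 | 80.0% |
| 5% | 76 | 78.7% |
| 10% | 72 | 76.2% |

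**3. Unbalanced loss at the expected result.** Expected events are 0.25 × 80 = 20 and 0.0875 × 80 = 7, so p = 0.006. Suppose that some tamsulosin patients and no placebo patients are untested, and that all seven tamsulosin events remain among those tested:

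| Untested on tamsulosin | Left out | p | Counted as retention | p |
|---|---|---|---|---|
| 1 | 20/80 vs 7/79 | 0.007 | 20/80 vs 8/80 | 0.013 |
| 2 | 20/80 vs 7/78 | 0.007 | 20/80 vs 9/80 | 0.024 |
| 3 | 20/80 vs 7/77 | 0.008 | 20/80 vs 10/80 | 0.043 |
| 4 | 20/80 vs 7/76 | 0.009 | 20/80 vs 11/80 | 0.072 |

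Left out, Fisher's test gives 0.010 to 0.011 over the same rows. Counted as retention, one untested placebo patient beside the four (21/80 vs 11/80) brings the chi-squared p back to 0.048. Fisher's test is stricter, giving 0.067 at three against none and 0.074 at four against one. The smallest expected cell in these tables is above 13, so chi-squared is the usual choice of the two.

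**4. Balanced loss.** With four untested in each arm, left out gives 20/76 vs 7/76, p = 0.006. Counted as retention gives 24/80 vs 11/80, p = 0.013. The verdict does not change.

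**5. False positives.** Take 25% in both arms, four tamsulosin patients left out and none on placebo. If a fraction f of those four would have failed, the expected rate among the 76 tested is (20 − 4f)/76. The exact chance of a significant result favouring tamsulosin is:

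| f | Rate among tested | Chance |
|---|---|---|
| 0.25 | 25.0% | 2.5% |
| 0.5 | 23.7% | 3.9% |
| 1 | 21.1% | 8.4% |

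With nobody missing, it is 2.6%.

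**The case for a change.** The strongest case for a change is that the gap is plain in the text, that the plan itself foresees admissions, and that closing it would take a few sentences and no extra patients or visits. Saying that patients will be tested states an intention; it is not a rule for when the intention fails. A cancelled operation or an undocumented test would leave the same hole. With four untested patients, all on tamsulosin, the choice between leaving them out (0.009) and counting them as retention (0.072) decides significance. A rule fixed in advance would remove the argument.

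The omission stands. The consequence is much weaker. The test follows within the same recovery stay, with no later visit to miss, and an unplanned admission can come after the test as easily as before it. The Background remark on same-day surgery describes the department's pelvic reconstructive work in general, not the sling patients enrolled here. No section links hypotension to skipping the test. The 0.072 needs a four-to-none split and a scoring rule that the plan does not contain. The 8.4% needs the same split with every one of the four a true failure. When a quarter of them would have failed, the rate assumed for everyone, there is no inflation. The added text would mainly write down the analysis that the plan already implies.

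**Conclusion.** No change to the plan follows. It omits a sentence on its analysis population and on missing results, and a statistician working from it would fill that gap sensibly: compare tested patients in the arm assigned, and report how many were untested in each arm and why, as far as the charts show.

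On that reading the size is small. Power is 78.7% at 5% loss and 76.2% at 10%, against 80.0% with none. The expected result stays at p = 0.009 or below with up to four untested patients, even if all are on tamsulosin.

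This rests on few patients missing the test. The documents support that, since the Methods give the test as the routine step after surgery, but they do not quantify it; the true number may be zero. It also rests on a two-sided 0.05 test, exactly 80 per arm and the plan's own rates. Many untested patients concentrated in one arm would be a different matter, but nothing in the documents points to that, and a count by arm in the trial report would show it.

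### Hypotension is listed only as a complication item with no blood-pressure values; adding the readings to the planned data pull would make that comparison considerably more sensitive.

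*Combined protocol and SAP*

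**What the plan says.** The secondary objective (Objectives) is to "evaluate for any differences in hypotension, unplanned admission, postoperative UTI, or unplanned 30-day healthcare encounters". Hypotension comes first in that list, but the items are not ranked. Specific Aim 2 limits it to the immediate postoperative period.

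Outcome measures, item 2a: "Determine differences in postoperative pain, hypotension, postoperative UTI after preoperative administration of tamsulosin compared with placebo". The next sentence gives the source for all three outcomes together: "This data will be obtained by electronic data pull and chart review". It does not say which source serves which outcome.

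In the Variables list, hypotension is one of four entries under "Immediate postoperative complications", beside uncontrolled nausea, uncontrolled pain and incisional bleeding. No blood-pressure reading, before or after the dose, is listed. Pain is treated differently: it has a complication entry and also numeric scores at ASU admission and at discharge.

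Statistical Methodology assigns no test to hypotension. It gives the general rule "Statistical significance will be defined at p-value < 0.05". The sample size paragraph in Methods concerns urinary retention only: "we will need to recruit 160 total subjects (80 per group").

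**The concern.** Blood pressure is a continuous measurement. If the trial keeps only whether each woman had hypotension, everything above or below the dividing line is lost, and the loss is greatest when the event is uncommon. No numeric cut is stated, so the event also could not be reproduced from the protocol by another team.

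At stake is how a null result would be read. The trial gives an alpha-blocker before mostly same-day surgery and names hypotension as something it will compare. If the comparison has little chance of showing a moderate fall in pressure, a non-significant p-value could pass for reassurance. Item 2a already plans an electronic data pull, so the more informative data may be obtainable at almost no cost.

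**Working it through.** **Inputs from the protocol.** 80 per arm, 1:1 (Methods); significance level 0.05 (Statistical Methodology), taken as two-sided because sidedness is not stated.

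**The plan's own figure.** The sample size is set "to evaluate for a 65% decrease in our urinary retention rate (from 25% to approximately 8.8"%), with 80% power. With unpooled variance, n per arm = (1.96 + 0.8416)² × (0.25×0.75 + 0.088×0.912) / (0.25 − 0.088)² = 80.1, which agrees with 80. The pooled-variance formula gives 83, and power at 80 per arm is then 78.6%. The figure reproduces, and it covers retention only. No rate, effect or power is stated for hypotension.

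**Assumed inputs (none in the documents).** Lowest recovery-area systolic is normal with SD 15 mmHg. The drug lowers the mean by 5 mmHg. The event is a value below 90 mmHg; this cut is purely illustrative and is not a proposed definition. The placebo mean is varied (115, 105, 100 mmHg) to vary the incidence. The correlation between pre-dose and lowest systolic is 0.5.

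**Event outcome.** Incidence is Φ((90 − mean)/15). Power is exact for the chi-squared test, by summing over all pairs of binomial counts with n = 80 per arm.
- Placebo mean 115: Φ(−25/15) = 4.8% vs Φ(−20/15) = 9.1%; power 17%.
- Placebo mean 105: Φ(−15/15) = 15.9% vs Φ(−10/15) = 25.2%; power 31%.
- Placebo mean 100: Φ(−10/15) = 25.2% vs Φ(−5/15) = 36.9%; power 36%.

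**Continuous outcome.** Power = Φ((d/SD) × √(n/2) − 1.96).
- Unadjusted: Φ(5/15 × √40 − 1.96) = Φ(0.148) = 56%.
- ANCOVA: the residual SD is 15 × √(1 − 0.5²) = 12.99, so Φ(5/12.99 × √40 − 1.96) = Φ(0.474) = 68%.

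**Sensitivity (placebo mean 115 unless stated).**

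| Scenario | Event | Continuous | ANCOVA |
|---|---|---|---|
| SD 20, fall 5 | 16% | 35% | 45% |
| SD 15, fall 7 | 33% | 84% | 93% |
| SD 15, fall 7, mean 105 | 56% | 84% | 93% |
| SD 15, fall 7, mean 100 | 62% | 84% | 93% |

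**Information kept by a cut.** For a normal variable cut at prevalence p, the share kept for small shifts is φ(z_p)² / [p(1 − p)]. At 5% this is 0.1031² / 0.0475 = 22%. It is 34% at 10%, 49% at 20%, 54% at 25% and 64% at 50%. A cut therefore keeps less than half only when incidence is below about 20%.

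**What 80 per arm can detect with 80% power.** As an event (normal approximation): 5% vs 19.4%, 10% vs 27.1%, or 20% vs 40.2%. As a mean: (1.96 + 0.8416) × √(2/80) = 0.44 SD, or 6.6 mmHg at SD 15.

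**The case against.** Four points can be made against this.

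1. The coding is inferred. The protocol never says that hypotension is recorded as yes/no, or that it counts only when staff chart it as a complication. The data pull may itself supply readings from which hypotension is classified. This stands, and a reader should not infer that charted coding is established. But even with such a pull, no cut is given and no reading is listed as a variable to be kept or analysed.

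2. The size depends on inputs the documents do not give. A reader might infer that the plan discards most of its ability to see a pressure effect, or that it would miss a real fall about four times in five. Neither follows from the documents. The first requires an incidence below about 20%. The second fits only the less favourable scenarios: with a 7 mmHg fall, the miss rate is 67% at 5% incidence and 38% at 25%. What does not change is the ordering, since the continuous comparison is clearly stronger in every scenario shown.

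3. The 17% is the power of a numeric cut applied to every patient, which is also the event recommended below. It does not measure under- or over-charting, for which the documents give no basis. So the gain comes from analysing the readings, not from redefining the event.

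4. A shift in mean lowest systolic is not clinical hypotension, which is what the objective names, and the lowest of several readings depends on how many were taken. Both are true. The continuous analysis must therefore supplement the event and cannot replace it.

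A reader might also take hypotension to be the trial's main safety outcome. The protocol names it first among its secondary items but does not rank it.

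**Conclusion.** The point holds as a worthwhile improvement. Hypotension has no numeric definition, and no blood-pressure value is listed for collection. If it is analysed as present or absent, which is the natural reading, 80 per arm gives about 17% power at 5% placebo incidence and 31-36% at 16-25%. The readings give 56%, or 68% with baseline adjustment. These figures rest on a normal model, SD 15 mmHg, a 5 mmHg fall and correlation 0.5, all assumed.

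The trial is not powered for hypotension in either form and does not claim to be; even the unadjusted continuous comparison falls short of 80% for a 5 mmHg shift at SD 15. The primary outcome and its sample size are unaffected.

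**What to change.** - **Variables:** add two fields to the planned electronic data pull, the last systolic pressure before the dose and the lowest recorded systolic in the recovery area.
- **Statistical Methodology:** report the between-arm difference in lowest systolic by ANCOVA on the pre-dose value, with a 95% CI, as a supplement to the hypotension event.
- **Outcome measures, item 2a:** derive the event from the same readings with one numeric cut, chosen by the investigators and fixed before unblinding. Keep the charted complication as a descriptive item.
- **Reporting:** give the number of readings or recovery time by arm, because the lowest value depends on how often and how long pressure was recorded. PACU and ASU times are already in the Variables list.

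The cost is two data fields and one more secondary analysis. No extra measurement is needed, assuming vital signs are held in the electronic record. The added analysis should be labelled secondary, and its mean difference should not be described as a difference in clinical hypotension.

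### The protocol places the 'feel empty' question after the bladder scan and does not require the answer before the PVR is known, so the Aim 5 association could be overstated

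*Combined protocol and SAP*

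**What the plan says.** All references are to the combined protocol and SAP.

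- **Methods, voiding trial.** The description opens "The voiding trial will be performed as follows: using a Foley catheter placed in the OR" and goes on to the retro-fill, removal of the catheter and the request to void. The next sentence covers the voided volume and the scan, and the question comes straight after it: "a bladder scan post-void residual (PVR) volume will be obtained. Patients will be asked if they" feel empty. Its stated purpose is to serve "as a subjective measure of voiding success". The definition of a failed trial follows.
- **Specific Aims, item 5.** "Evaluate subjective measure of “feeling empty” after a void compared with PVR value".
- **Outcome measures, item 2d.** "Determine correlation between subjective measure of “feeling empty” and PVR". The answer is to be "documented in the electronic medical record by the postoperative nursing staff along with the PVR result obtained from ultrasound".
- **Methods, randomization.** Clinicians, nursing staff and patients are blinded to the trial group and medication. Masking to the PVR is not mentioned.
- **Variables.** The answer on feeling empty is listed. The time at which the question was put, and whether the PVR was known by then, are not.

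**The concern.** Aim 5 is informative only if the patient reports her sensation independently of the measurement it will be compared with. A recovery nurse who works through the Methods paragraph in its written order would scan first and ask second. By then the nurse, the patient or both could know the residual volume.

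The result also matters to the patient. The PVR is one of the two components of the failure rule, failure means going home with a catheter, and the Background section says that many women see this as a complication. A patient who has learned that much urine remains may be less inclined to say that she feels empty. A nurse who knows the figure may phrase the question, or chart a doubtful reply, in line with it.

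Blinding to treatment does not help here, because the information at issue is the PVR and not the allocation. At stake is the conclusion from outcome 2d: a reader could take the sensation of emptying to track the PVR more closely than it does.

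**Working it through.** **Does the plan secure independence?** The documents give no figure for agreement between the answer and the PVR, so there is nothing to reproduce. The main check is a reading of the text.

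| Condition | What the documents give |
|---|---|
| Question placed before the scan | No. In Methods it is written after the scan. |
| Order fixed elsewhere | No. Aim 5 says "after a void compared with PVR value", which fits either order. |
| Answer charted before the PVR is known | Not required. Outcome 2d has the two documented together. |
| Patient or staff masked to the PVR | Not mentioned. |
| Data to identify affected answers later | Not among the listed variables. |

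None of the conditions that would protect the comparison is present.

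**Direction.** Suppose a share q of patients give the answer that matches the scan result and the rest answer independently of it. Sensitivity (Se) and specificity (Sp) of 'not empty' then become

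- Se(q) = Se + q(1 − Se)
- Sp(q) = Sp + q(1 − Sp)

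Both can only rise with q, so influence of this kind raises apparent agreement.

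**Illustration, with assumed inputs.** Only the prevalence draws on the protocol. With 80 per group, 25% retention in one arm and a 65% reduction in the other (0.25 × 0.35 = 0.0875), failures number 20 + 7 = 27, so π = 27/160 = 0.169. This supposes that the hoped-for effect occurs. Se = 0.60, Sp = 0.85 and q are assumptions.

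Formulas:

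- observed agreement: po = π·Se + (1 − π)·Sp
- share answering 'not empty': m = π·Se + (1 − π)(1 − Sp)
- chance agreement: pe = π·m + (1 − π)(1 − m)
- kappa = (po − pe)/(1 − pe)

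At q = 0: po = 0.101 + 0.707 = 0.808; m = 0.226; pe = 0.682; kappa = 0.126/0.318 = 0.40.

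At q = 0.25: Se = 0.70, Sp = 0.8875; po = 0.856; m = 0.212; pe = 0.691; kappa = 0.165/0.309 = 0.53.

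The same formulas with other assumed values:

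| Assumed inputs | q = 0 | q = 0.10 | q = 0.25 | q = 0.50 |
|---|---|---|---|---|
| Se 0.60, Sp 0.85, π = 27/160 | 0.40 | 0.45 | 0.53 | 0.68 |
| Se 0.50, Sp 0.80, π = 0.169 | 0.25 | 0.32 | 0.42 | 0.59 |
| Se 0.70, Sp 0.80, π = 0.169 | 0.39 | 0.44 | 0.52 | 0.66 |

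These values show direction only. Kappa here is agreement with a yes/no result, whereas outcome 2d plans a correlation with the PVR. In the first row that result is pass/fail, which also depends on the voided volume.

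**The case against.** The strongest reply is that the protocol never says the question comes after the scan. The phrase that introduces the steps opens a sentence that ends with the request to void. The measurements and the question stand in two later sentences, with no linking word to order them. The paragraph is not strictly chronological either, since the next sentence defines failure. Aim 5 ties the sensation to the void, which is compatible with asking first. This stands: the order is inferred from sentence sequence. It does not remove the point, because if the sequence was not meant as an order, the protocol is silent on the one condition that Aim 5 needs.

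A reader might also infer more than the documents support:

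- *That one nurse scans, asks and records.* Outcome 2d refers to nursing staff in general, and no section says who performs the scan. Charting two items together does not show when the question was put.
- *That the scan alone decides whether the patient goes home with a catheter.* The failure rule in Methods combines voided volume with PVR.
- *That agreement will be inflated.* This requires the result to be disclosed or cued, and the documents do not say whether it is.
- *That the kappa values estimate the bias in this trial.* Sensitivity, specificity and the influenced share are all assumed.

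The reach is also narrow. Outcome 2d is the last of the secondary outcomes, is not a comparison between arms, and is absent from the stated secondary objective.

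**Conclusion.** The point holds as a gap in the measurement procedure. As written, the question follows the scan, and nothing keeps the answer independent of the PVR. If the PVR is known or cued when the patient answers, the association in Aim 5 and outcome 2d could be overstated. Analysis could not put this right, because the listed data would not show which answers were affected.

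The verdict rests on two assumptions that the documents neither confirm nor exclude: that staff follow the order of the text, and that the result reaches the patient or shapes how the answer is elicited or charted. The size of any overstatement cannot be derived from the documents.

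The answer does not enter the pass/fail rule, so the primary outcome and the sample size of 160 are untouched. This is a minor point and a free improvement, held with moderate confidence.

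**What to change.** In the Methods description of the voiding trial, move the question so that it follows the void. State that the patient is asked whether she feels empty, and her answer is charted, before the bladder scan is done and before any volume or result is mentioned. Put the same order in outcome 2d.

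The cost is one reordered sentence, one added clause and a line in the recovery nurses' instruction. The question and the scan stay the same, with no added staff, visits, tests or patients. The pass/fail rule and patient care do not change.
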